13.3 Plan of Analysis

Demographic and clinical characteristics of patients and the characteristics of treated lesions (volume, location, and modality) will be summarized by means, medians, standard deviations, ranges and proportions as applicable. Toxicities will be tabulated by type and grade at each follow-up interval. All adverse events will be reported to the SKCCC Data Safety Monitoring Committee and the JHH IRB. The study may be stopped before reaching the accrual goal at the recommendation of any of these groups. The level of progression free survival (and other categorical outcomes) will be tabulated at each follow-up interval. The percentage of individuals free from local progression will be computed with exact 95% confidence intervals. Time to event outcomes (overall survival, metastasis free survival, and progression free survival) will be summarized using Kaplan-Meier curves and medians with 95%

confidence intervals calculated using Greenwood's formula. A competing risks analysis of local progression at 6, 12, and 18 months will be conducted. The measurements of the volume of the pancreatic tumors based upon CT and/or PET-CT scans will be compared using paired t-tests or Wilcoxon signed-rank tests as appropriate. Quality of life at each interval will be calculated and compared using the recommended guidelines from the module (available by E-mail: [contact]). [name] from MD Anderson will also help with data analysis. Data will be transferred via secure JH Box and totally anonymized.

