11.1.6 Progression-Free Survival (or other parameters)

The criteria for time to progression and progression-free survival (PFS) will be the duration from Linac based SBRT treatment to documented local/regional or distant progression or death. Local PFS will be measured as the duration from Linac based SBRT treatment to local progression or death from any cause.

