13.6 Data Analysis

We will perform separate analyses for Cohorts A and B. Descriptive summary statistics (mean, median, standard deviation, range, or proportion) will be presented for demographic and clinical characteristics of patients or treated lesions.

Toxicity will be summarized by type and grade for each cohort. The rate of grade 3 or higher GI toxicity will be estimated along with its 95% CI. This study will evaluate the efficacy of fractionated Linac based SBRT based on local-regional progression free survival (LFSP). LPFS is defined as the elapsed time from the start date of Linac based SBRT treatment to the date of documented local/regional tumor progression or death, whichever occurs first. We will plot the Kaplan-Meier curve for LPFS and estimate 1-yr local control and its 95% confidence interval based on KM estimate and Greenwood's formula. In addition, we will consider death without local progression as a competing event, and estimate cumulative incidence rate of local-regional progression using a competing risk analysis.

Other outcomes to be studied in this group of patients include, overall survival (OS), progression free survival (PFS) and quality of life. OS is defined as the elapsed time from the start date of Linac based SBRT treatment to death due to any cause; PFS is the time from the start date of Linac based SBRT treatment to disease progression or death, whichever occurs first. OS and PFS will be summarized using Kaplan-Meier plot.

Quality of life will be assessed via EORTC QLQ-C30 (v3.0) questionnaires. Our study population is pancreatic cancer subjects, and the analysis will be focused on Global Health Status/QoL scale, symptom scale (fatigue, pain), and functional scale (physical functioning, role functioning, emotional functioning). For each module, summary statistics of the score will be reported as baseline and follow up time. Changes of quality of life score before and after treatment will be tested via paired t-test. In addition, mixture effect models will be fitted for accessing the quality of life changes over time. The frequency of patients who reach minimal clinically important difference of 10-points change from baseline will be tabulated by time. The time to definitive deterioration in quality of life will be analyzed using the Kaplan Meier method.

REFERENCES

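### The exact-interval percentage free from local progression in 13.3 cannot handle patients of unknown local status, and 13.6 labels Kaplan-Meier LPFS as local control; neither section says which result is the local-control estimate

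*Combined protocol and SAP*

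**What the plan says.** Section 13.3 gives two summaries of local progression. The first is a percentage: "The percentage of individuals free from local progression will be computed with exact 95% confidence intervals". The sentence names no time point, no denominator and no rule for patients whose local status is unknown. The second is "A competing risks analysis of local progression at 6, 12, and 18 months will be conducted". The Kaplan-Meier list in the same section leaves out local PFS: "Time to event outcomes (overall survival, metastasis free survival, and progression free survival) will be summarized using Kaplan-Meier curves".

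Section 13.6 gives two more. One is a Kaplan-Meier analysis: "We will plot the Kaplan-Meier curve for LPFS and estimate 1-yr local control and its 95% confidence interval", with limits from Greenwood's formula. The other is a competing-risks analysis in which "we will consider death without local progression as a competing event", used to "estimate cumulative incidence rate of local-regional progression using a competing risk analysis".

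Section 11.1.6 defines the endpoint behind the Kaplan-Meier curve: "Local PFS will be measured as the duration from Linac based SBRT treatment to local progression or death from any cause". Section 13.2 sets the efficacy population as everyone who finishes SBRT and does not require a follow-up scan. The synopsis hypothesises local control of 80-90% at one year.

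**The concern.** An exact interval for a percentage is binomial: each patient counted must be a known yes or no. In this population some patients will have unknown local status. Section 6.4 expects some to become too ill to travel, and withdrawal is possible under 6.5. A crude percentage cannot censor such patients. They must be counted as free, counted as failed, or dropped, and 13.3 does not say which.

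The label in 13.6 is a separate fault. LPFS falls with every death, whether or not the tumour was controlled. Freedom from local progression does not. If the LPFS figure is reported as local control, it will be read against the 80-90% hypothesis, which is about something else.

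The plan thus offers three figures that could each be presented as one-year local control: the percentage, Kaplan-Meier LPFS, and 1 minus cumulative incidence. With no order fixed in advance, the choice could be made after the results are seen.

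**Working it through.** **1. The plan's own efficacy figure.** Section 13.4.2 states 89% power (cohort A, one-year LPFS 30% to 45%) and 90% (cohort B, 50% to 65%), with 60 patients per cohort, one-sided 0.04, exponential times, 2.5 years of uniform accrual and 1 year of follow-up.

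- Hazard: λ = −ln(one-year LPFS).
- Expected events: d = 60 × [1 − (e^(−λ) − e^(−3.5λ)) / (2.5λ)].
- Power: Φ{[ln(λ0/λ1) − 1.751/√d0] × √d1}.
- Cohort A: λ0 = 1.204, λ1 = 0.799, d0 = 54.3, d1 = 48.3, power 88.6%.
- Cohort B: λ0 = 0.693, λ1 = 0.431, d0 = 45.7, d1 = 36.1, power 90.4%.

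Both figures reproduce. A one-year binomial percentage with the same 60 patients and alpha gives 76.5% and 72.6% (normal approximation) or 74.1% and 66.2% (exact). The design therefore rests on a time-to-event analysis.

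**2. Effect of loss on the percentage.** The documents give no loss rate, so one-year loss of 10%, 20% and 30% is assumed. Local progression, death and loss are taken as independent and exponential, with hazards λL, λD and λC = −ln(1 − loss), and Λ = λL + λD + λC.

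- Percentage over all treated, unknowns counted as free: 1 − (λL/Λ)(1 − e^(−Λ)).
- True freedom from local progression (1 minus cumulative incidence): the same with λC = 0.

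Example: cohort A at its target LPFS of 45%, with events assumed to split equally between local progression and death, and 20% loss. λL = λD = 0.399, λC = 0.223, Λ = 1.022, e^(−Λ) = 0.36. Percentage = 1 − 0.391 × 0.64 = 75.0%. True value = 1 − 0.5 × 0.55 = 72.5%.

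| Scenario | True | 10% loss | 20% loss | 30% loss |
|---|---|---|---|---|
| A, LPFS 45%, equal split | 72.5% | 73.7% | 75.0% | 76.3% |
| B, LPFS 65%, equal split | 82.5% | 83.3% | 84.2% | 85.1% |
| 25% net local failure, 40% one-year survival | 83.3% | 84.0% | 84.7% | 85.4% |

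The upward bias is about 1-4 points. Simulation of the two cohort scenarios, with 400,000 patients each, agrees to within about 0.1 point. In the extreme case of no deaths, 30% loss moves cohort A from 45% to about 53% and B from 65% to about 70%. With no loss, the percentage equals 1 minus cumulative incidence, so deaths alone do not separate the two.

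The interval has the same defect. For 50 of 60 free (83%), the exact limits are 71.5-91.7%, whether or not all 60 statuses were observed.

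**3. Effect of the label in 13.6.** Assume 25% net local failure (λL = 0.288) and vary one-year survival. LPFS = 0.75 × survival. Local control = 1 − [λL/(λL + λD)] × (1 − LPFS).

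| One-year survival | LPFS | 1 minus cumulative incidence |
|---|---|---|
| 21% | 16% | 87% |
| 40% | 30% | 83% |
| 50% | 38% | 82% |

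At 40% survival: λD = 0.916, and 1 − (0.288/1.204) × 0.70 = 0.833.

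One check needs no model. Because death is an event, LPFS cannot exceed overall survival. The single-fraction series in section 3.3 reports 84% freedom from local progression at 12 months with 21% overall survival, so an LPFS that counts deaths could be at most 21% there. The plan's own LPFS targets, 45% and 65%, also lie well below 80-90%.

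**The case against.** The strongest reply is that little turns on the percentage. The primary endpoint is late toxicity, and efficacy power and interim futility use LPFS. Competing risks, the suitable method, is already in both 13.3 and 13.6. The loss rates are assumed, and the plan works against loss: post-SBRT CT is mandatory (8.2.1.1), and outside evaluations and records are accepted (6.4 and the study calendar). A bias of 1-4 points is small beside an exact interval about 20 points wide at 60 patients. All of this stands, and it limits the point to a secondary endpoint.

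Three stronger readings are tempting, and the documents do not support them.

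- A reader might infer that the plan counts lost or unscanned patients as controlled. It does not say so; their handling is undefined. A denominator restricted to patients who progressed or were followed progression-free to one year would bias the figure downward instead.
- A reader might compare all treated patients with those still seen at 12 months and find a gap of 8-16 points. No section proposes the second denominator, and 13.2 points to all treated.
- A reader might say that 13.3 and 13.6 contradict each other. LPFS and freedom from local progression are different quantities, so the sections are unreconciled rather than contradictory.

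What the reply does not remove is that 13.3 names an interval method unsuited to censored data, 13.6 attaches the wrong name to an estimate, and nothing sets precedence.

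**Conclusion.** The point holds in a limited form. The percentage with exact limits has no means of handling unknown local status. If all treated patients are the denominator and unknowns are not recorded as progressed, it overstates local control by about 1-4 points. That size rests on assumed non-informative loss of 10-30%, exponential times and assumed shares of progression and death.

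The label in 13.6 has the larger consequence: about 30% against 83% in the example with 25% net local failure and 40% one-year survival. The direction needs no assumption, because LPFS counts deaths that local control does not. The missing order of precedence leaves the reported figure open to choice. The primary toxicity design and the LPFS power and futility rules are unaffected.

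**What to change.** In 13.3, delete the sentence on the percentage with exact limits. State in its place that local control at 6, 12 and 18 months is 1 minus the cumulative incidence of local progression. Treat death before local progression as the competing event, censor lost or withdrawn patients at their last adequate CT, and take the confidence interval from that estimator's variance. Report the numbers at risk and the number of patients never re-scanned.

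In 13.6, call the Kaplan-Meier and Greenwood result one-year LPFS, and refer to 13.3 for local control.

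The cost is wording only: the competing-risks analysis is already planned, and no new visits, data or patients are needed. The downside is that the reported local-control figure may be slightly less favourable.

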	STEREOTACTIC BODY RADIATION
	THERAPY (SBRT) FOR PALLIATIVE
	MANAGEMENT OF UNRESECTABLE
	RECURRENT OR RESIDUAL PANCREATIC
	OR PERIAMPULLARY ADENOCARCINOMA
STUDY PHASE	II
INDICATION	Unresectable recurrent or residual pancreatic or
	periampullary tumors
PRIMARY OBJECTIVE	• To evaluate rates of late (> 3 months after treatment) gastrointestinal toxicity following fractionated Linac based SBRT for pancreatic tumors. Toxicities of note include grade 2 or greater gastritis, enteritis, fistula, or ulcer and any other grade 3 or greater gastrointestinal toxicity.
SECONDARY OBJECTIVES	• To evaluate rates of acute (within 3 months of treatment) gastrointestinal toxicity following fractionated Linac based SBRT for pancreatic tumors. Toxicities of note include any grade 3 or greater gastrointestinal toxicity.
	• To evaluate local progression free survival, overall survival, metastasis-free survival, and progression-free survival rates following Linac based SBRT in patients with unresectable recurrent or residual pancreatic or periampullary adenocarcinoma.
	• To evaluate the ability of Linac based SBRT to provide pain control among symptomatic patients as measured by pain medication requirement at 3, 6 and 12 months after treatment.
	• To evaluate the utility of FDG-PET for treatment planning and estimation of progression-free survival.
	• To develop and standardize Linac based SBRT delivery and dosimetric parameters.
	• To evaluate toxicity and outcomes among two cohorts of patients: a) patients with recurrent or residual disease after previous chemoradiation therapy, with or without surgery, who will be treated with 5 Gy x 5 and (b) patients with recurrent or residual disease after chemotherapy only, (with or without surgery), who will be treated with 6.6 Gy x 5.
HYPOTHESES	No standard treatment option has yet been
	established for patients with recurrent or residual
	disease after definitive treatment of pancreatic or

	periampullary cancers (duodenal, ampullary, bile
	duct). Linac based stereotactic body radiation
	therapy (SBRT) administered in 1-3 fractions has
	been shown to be an effective treatment option for
	patients with unresectable, locally advanced
	pancreatic adenocarcinoma, achieving local control
	rates of 84-92% at one year. Associated late
	gastrointestinal toxicity rates have been reported to
	be 22-25% at 1 year. We hypothesize that similarly
	excellent local control rates (80-90% at one year)

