SAMPLE SIZE BY TREATMENT CROUP	 toxicity. Secondary Endpoints: Acute (within 3 months of treatment) grade 3 or greater gastrointestinal toxicity. Local progression free survival, progressionfree survival, metastasis-free survival, and overall survival rates at 3, 6, and 12 months after therapy. Symptom control as measured by pain medication requirement at 3, 6, and 12 months after Linac based SBRT. Change in pancreatic or periampullary tumor volume with FDG-PET/CT compared to CT scan. Health-related quality of life (QoL) before and after SBRT.
SAMPLE SIZE BY TREATMENT GROUP	 toxicity. Secondary Endpoints: Acute (within 3 months of treatment) grade 3 or greater gastrointestinal toxicity. Local progression free survival, progressionfree survival, metastasis-free survival, and overall survival rates at 3, 6, and 12 months after therapy. Symptom control as measured by pain medication requirement at 3, 6, and 12 months after Linac based SBRT. Change in pancreatic or periampullary tumor volume with FDG-PET/CT compared to CT scan. Health-related quality of life (QoL) before and after SBRT. 120 (60 in Cohort A, 60 in Cohort B; see inclusion criteria below for cohort definitions)

CRITERIA	
INCLUSION CRITERIA	• Age >18 years.
	 Karnofsky Performance Status ≥70% (see Appendix II).
	• Histologically confirmed pancreatic or periampullary adenocarcinoma; at least the majority of the histopathologic specimen must be identified as adenocarcinoma. If previously diagnosed, recurrence can be based on imaging findings of recurrence.
	• Either: (a) Previously completed standard of care or protocol treatment for pancreatic or periampullary adenocarcinoma consisting of either surgical resection with neoadjuvant/adjuvant CRT for resectable disease or conventional CRT as definitive treatment for unresectable disease. These patients who have received prior radiation therapy will constitute Cohort A and will receiver SPBT as 6 Curve 5
	 receive SBRT as 5 Gy x 5. OR (b) Previously initiated standard of care or protocol treatment for pancreatic or periampullary adenocarcinoma consisting of chemotherapy (without radiation) for unresectable disease or surgical resection with neoadjuvant/adjuvant chemotherapy (without radiation) for resectable disease. Patients who have not previously received radiation therapy will constitute Cohort B and will receive Linac based SBRT as 6.6 Gy x 5.

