- 6) Motion management can be addressed using respiratory gating, breath-hold, respiratory tracking, or abdominal compression. Specialized compression belts may be utilized for some patients. They come in 4 sizes: S, M, L, and XL. Each belt has an adjustable pressure cuff which can be used to reduce breathing motion. Fluoroscopy is used to assess motion of implanted gold markers before and after compression. The goal is to reduce motion from typically 11-22 mm peak to less than 5 mm. If the fiducial motion cannot be decreased to 5 mm or less, then respiratory gating using either the Varian Respiratory Management (RPM) system or the Elekta Active Breathing Coordinator (ABC) will be utilized for treatment delivery. Prior to simulation, standard guidelines will be followed.
- 7) As long as the specified dosimetric parameters for SBRT are reached, patients may be treated on any IGRT-enabled machine.
- 8) All patients must start Linac based SBRT within 4 weeks of the simulation scan.
- 6.1.3 Treatment Planning
 - 1) When available, an FDG-PET scan is preferred for treatment planning purposes and will be acquired on a flat table top with the same immobilization devices used for the treatment planning CT simulation.
 - An SBRT treatment plan will be developed using Pinnaclebased on tumor geometry and location. Institutional standards for radiation quality assurance and radiation delivery will be utilized.
 - 3) The tumor volume (GTV), as identified on the treatment planning CT, will be contoured by an attending physician from Johns Hopkins Hospital. The final GTV will be defined by the attending radiation oncologist after reviewing the diagnostic CT, respiratory-correlated 4D-CT scan, pancreas protocol CT, and/or the FDG-PET/CT scan. These scans will be used to define the ITV (internal target volume). The final PTV (planning treatment volume) expansion will consist of an additional 2-3mm of margin expansion, except if the margin results in expansion into the duodenum or stomach. In these cases, margin expansion is allowed to be non-uniform. The dose will be prescribed to the isodose line that completely surrounds the PTV. It is recommended that 6-12 co-planar fields be used in the radiation treatment plan.
 - 4) Contours of the fiducials used for target localization will be generated on the applicable image sets, to be used for patient setup on treatment.

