8.1.1.4 Coding of specimens for privacy protection

At the time of consent, each patient will be given a specific confidential identification number (IDN). Specimens will be stored under the patient's IDN. The information can be shared with other investigators listed on this protocol. Study data will be maintained in password protected computer files (protected online database through Johns Hopkins). Only research personnel will have access to this information.

8.2 Collection of Pre and Post Treatment CT/PET Scans, Treatment Planning Scans, and Treatment Plans

- 8.2.1 Data and Image Collection
 - 8.2.1.1 Pre-Linac based SBRT PET scan is recommended but not required. Post SBRT PET scans will be optional for all patients based on the opinion of the treating physician. Pre- and post-Linac based SBRT CT scans will be mandatory for all patients (PET/CT may supplement protocol CT). All images (CT and PET) will be stored electronically by JHU through the Oncospace network and be registered to each patient using the IDN. Radiation treatment plans will also be retrospectively reviewed and stored at JHU via Oncospace. The JHU database is set up to store ROI geometries and dose distributions along with the CT. This design facilitates the investigation of dosimetric effects on tumor response and complications utilizing DVH or other attributes of the 3D dose.

For Pinnacle, the data can be directly placed in the JHU database via scripts.

- 8.2.1.2 All treatment planning scans will be stored electronically by JHU through the Oncospace network and be registered to each patient using the IDN. Specific parameters will be prospectively collected such as treatment volume and dose to adjacent structures in oncospace
- 8.2.1.3 Dynamic Whole Body PET/CT

Up to 17 patients will be recruited to a sub-project that will assess the feasibility of acquiring a quantitative dynamic whole body PET/CT early after treatment. The aim of this sub-project is to assess the extent to which dynamic PET can be used to aid in the discrimination of tumor from radiation induced inflammation in a therapy assessment setting. This could potentially enable future PET/CT-based response assessment at an earlier time than the current protocol and clinical practice, 4-6 weeks post-treatment. This will allow therapy decision (success or failure) to be made earlier and management is personalized.

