13. STATISTICAL CONSIDERATIONS

13.1 Endpoints

13.1.1 Primary Endpoint

To evaluate late (>3 months after Linac based SBRT) grade 2 or greater gastritis, fistula, enteritis, or ulcer, or any other grade 3 or greater gastrointestinal toxicity attributable to fractionated Linac based SBRT.

- 13.1.2 Secondary Endpoints
 - To determine rates of local progression free survival, overall survival, metastasis-free survival, and progression-free survival at 3, 6, and 12 months from Linac based SBRT.
 - To evaluate acute toxicity, defined as any grade 3 or greater gastrointestinal toxicity within 3 months of treatment.
 - To use FDG-(if available as per the recommendation by your treating physician) /CT scans for assessment of tumor response and progression.
 - To evaluate the role of FDG-PET scans in treatment planning.
 - To assess the quality of life before and after fractionated Linac based SBRT.
 - To further standardize Linac based SBRT delivery and dosimetric parameters.
 - To compare toxicity and outcomes among patients treated with fractionated Linac based SBRT delivered as 5 Gy x 5 (Cohort A of current protocol), 6.6 Gy X 5 (Cohort B of current protocol), 25 Gy X 1 (previous study), and 5-10 Gy x 3 (previous study).
 - To evaluate pain control (as define by pain medication requirements at 3, 6, and 12 months following Linac based SBRT.

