The sample size is 60 patients per cohort. The primary outcome used to determine the sample size is the percentage of individuals with a late gastrointestinal toxicity (grade 2-4) at one year. The late grade 2 or greater toxicity rates was previously observed for other treatment regiments for locally advanced pancreatic cancer were approximately 40%. We hypothesize that in each cohort, the toxicity rate for this regimen will be 20%, a 50% reduction. The stopping rules for futility were calculated based upon a two-stage design with a total sample size of 60 and an interim analysis of 16 patients (note: accrual will continue while interim analysis is being conducted). Within 16 patients, if 7 or more patients have late grade 2 or greater gastritis, enteritis, fistula, ulcer, or late grade 3 or greater GI toxicity, the trial will be stopped. If 6 or fewer patients have late grade 2 or greater gastritis, enteritis, fistula, ulcer, or late grade 3 or greater GI toxicity, then the study will continue enrolling patients until 60 patients have been accrued. After 60 patients are enrolled, if 17 or more of the patients have late grade 2 or greater gastritis, enteritis, fistula, ulcer, or late grade 3 or greater GI toxicity, the null hypothesis will not be rejected. If 16 or fewer of the patients have late grade 2 or greater gastritis, enteritis, fistula, ulcer, or late grade 3 or greater GI toxicity, we will conclude that one year late toxicity is below 40%. This design will reach 91% power with 2% type I error for grade 2 or greater late toxicity, and the probability of early termination is 0.47. In addition, this sample size will reach 89% and 90% power to test the increase of 1-year local progression free survival from 30% to 45% in cohort A and 50% to 65% in cohort B, respectively.

The calculation is based on a one-sided test at significance level 0.04, assuming exponential distribution for local progression time and 2.5 year uniform accrual time with 1 year follow up.

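### The paired test planned for CT versus PET-CT tumour volume addresses a systematic difference but does not show how far the two volumes differ within patients, which the treatment-planning objective needs

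*Combined protocol and SAP*

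**What the plan says.** The synopsis lists as an objective "To evaluate the utility of FDG-PET for treatment planning and estimation of progression-free survival". Section 13.1.2 repeats the planning part: "To evaluate the role of FDG-PET scans in treatment planning". The matching secondary endpoint in the synopsis is "Change in pancreatic or periampullary tumor volume with FDG-PET/CT compared to CT scan".

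The analysis is one sentence in Section 13.3: "The measurements of the volume of the pancreatic tumors based upon CT and/or PET-CT scans will be compared using paired t-tests or Wilcoxon signed-rank" tests, whichever is appropriate. Section 13.6 adds nothing on PET. The response rules in Section 11.1.2, including PERCIST, work patient by patient, but they concern response and progression after treatment rather than the planning target.

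Two further statements bear on what can be computed. Section 6.1.3 describes one final GTV, "defined by the attending radiation oncologist after reviewing the diagnostic CT, respiratory-correlated 4D-CT scan, pancreas protocol CT, and/or the FDG-PET/CT scan". Section 8.2.1.1 makes the baseline PET optional: "Pre-Linac based SBRT PET scan is recommended but not required".

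**The concern.** Treatment planning is done one patient at a time. To judge what PET contributes, a reader needs to know how much the PET-CT volume departs from the CT volume in a typical patient, and how widely that departure varies. A paired t-test asks whether the mean difference is zero. The signed-rank test asks the same of the centre (pseudo-median) of the differences. Neither describes the spread, so large differences in opposite directions can cancel, and a small but consistent difference can be highly significant.

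The plan has no limits of agreement, no estimated ratio with a confidence interval, no threshold for a relevant change and no expected number of paired scans. At stake is whether a stated secondary objective gets an informative answer from volumes that will be measured anyway.

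**Working it through.** The plan states no power, SD, effect size or threshold for this comparison, so there is no figure of its own to reproduce. Everything below is illustrative.

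**Inputs from the documents**
- Test: paired t or Wilcoxon signed-rank (Section 13.3).
- Ceiling on pairs: "The sample size is 60 patients per cohort" (Section 13.4.2), with the cohorts analysed separately (Section 13.6). PET is optional, so 60 pairs per cohort is a maximum.

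**Assumptions**
- SD of the per-patient log ratio of PET-CT to CT volume: 0.3, 0.4 or 0.5.
- A low case of 18 pairs. The only 18 in the documents is the number of patients with PET before and after SBRT in the group's earlier 32-patient trial (Section 3.3). That is a different pairing, so 18 is only an example.
- Two-sided 5% level.

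**1. Spread of individual ratios when the mean ratio is 1.** Limits = exp(±1.96 × SD).
- SD 0.3: exp(±0.588) = 0.56 to 1.80
- SD 0.4: exp(±0.784) = 0.46 to 2.19
- SD 0.5: exp(±0.980) = 0.38 to 2.66

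In all three cases the paired test is significant about 5% of the time. That is simply its type I error rate. The point is that the rate is the same at every spread, so the p-value carries no information on which case applies.

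**2. The same check on the percentage scale.** The per-patient PET-CT minus CT difference is taken as normal, with 20% as an assumed relevant change and 20, 40 or 60 pairs. The t-test was simulated 20,000 times and the Wilcoxon test 1,500 times.

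| Mean difference | SD | Either test significant | Patients differing by more than 20% |
|---|---|---|---|
| 0% | 10% | about 4-6% | 4.6% |
| 0% | 20% | about 4-6% | 31.7% |
| 0% | 30% | about 4-6% | 50.5% |
| 5% | 5% | about 99-100% | 0.14% |

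The significance rate does not track how often the volumes differ materially, in either direction.

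**3. Power for a true 10% difference.** Noncentral t with n − 1 degrees of freedom and noncentrality ln(1.1) × √n / SD, where ln(1.1) = 0.0953.

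| SD of log ratio | 18 pairs: noncentrality, power | 60 pairs: noncentrality, power |
|---|---|---|
| 0.3 | 1.35, 25% | 2.46, 68% |
| 0.4 | 1.01, 16% | 1.85, 44% |
| 0.5 | 0.81, 12% | 1.48, 31% |

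**4. Precision of the proposed alternative.** The 95% CI half-width of each limit of agreement is t × √(1/n + 1.96²/(2(n − 1))) × SD. This gives 0.81 SD with 20 pairs, 0.55 SD with 40 and 0.44 SD with 60. At SD 0.4 with 60 pairs, the upper limit of 2.19 would carry a CI of exp(0.784 ± 0.444 × 0.4), which is 1.83 to 2.62.

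**The case against.** **The endpoint as worded asks about volume change, and a paired test is a conventional answer to it.** This stands. A significant result would support a systematic difference between modalities. A reader might infer that the planned analysis can say nothing either way on the secondary endpoint, but the endpoint wording does not support that. The gap is against the treatment-planning objective.

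**The sentence in Section 13.3 may mean volumes before and after treatment, on either modality.** The wording allows this, and Section 11.1 does compare post-treatment scans with the pretreatment scan. The synopsis endpoint favours the between-modality reading. Under the other reading the planning comparison would have no analysis at all. Either way the sentence needs clarifying.

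**Low power comes from optional PET, not from the choice of test.** This is correct, and limits of agreement from few pairs would also be imprecise. The low power is a reason to report an estimate with its interval, not evidence against the test itself. Pooling both cohorts (120 pairs, SD 0.4) would give 74%, but Section 13.6 plans separate analyses.

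**A reader might infer that a non-significant result will be taken to mean that PET adds nothing.** The plan states no such rule.

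**A reader might also infer that a spatial overlap measure is free because the contours are stored.** The documents do not show this. Section 6.1.3 describes a single final GTV set after all available scans have been reviewed, and Section 8.2.1.1 mentions stored ROI geometries with the CT but no separate CT-only and PET contours. An overlap computed from a GTV drawn with PET in view would be contaminated.

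**Conclusion.** The concern holds in a limited form. The only planned analysis of CT against PET-CT volume addresses the centre of the differences. It leaves out the within-patient spread, which the planning objective needs. That conclusion rests on the text and on what the tests measure.

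The figures in the working depend on the assumed SDs, the assumed 18 pairs and the assumed 20% threshold, none of which the documents supply. They show that the spread could matter, not that it does in these patients.

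This is a desirable improvement to one secondary analysis. It has no bearing on the primary toxicity decision or on the local progression-free survival rules.

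**What to change.** In Section 13.3:
- State that the comparison is between modalities, on pre-SBRT scans, in patients who have both.
- Report the number of such pairs in each cohort.
- Report the geometric mean PET-CT/CT volume ratio with its 95% CI.
- Report Bland-Altman 95% limits of agreement on the log ratio, back-transformed, with CIs for the limits.
- Keep the paired test as secondary.
- Report the percentage of the PET volume lying outside the CT-defined GTV only where separate CT-only and PET contours exist.

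**Cost.** All but the last item use the same paired volumes as the planned test, so the change is wording and a little extra analysis. The limits will be imprecise if few patients have PET, and the CIs will show this. Extending the overlap measure to all patients with PET could require separate contouring under Section 6.1.3 or re-contouring of stored images, and is not needed for the main fix.
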